STUDY TITLE: Evaluation of Bridge Device in Pain Management for Outpatient Rotator Cuff Surgery

IRB: STUDY23030139

NCT06071884

Protocol & Statistical Analysis: 18 SEP 2023

Proposal: Use of the "Bridge" device for pain management after ambulatory rotator cuff repair.

Investigators: [name] (CA2), [name], [name] (CBY), [name], [name], [name]

Background:

Peripheral nerve blocks are effective for pain of shoulder surgery, including rotator cuff repair. However, single shot blocks are limited in duration, and their termination leads to rapid resumption of pain, sometimes termed "rebound" pain (1.). Catheters are more effective in providing long term pain control, but generally are removed by postoperative day three to avoid infection and due to pump reservoir limitations. In addition, they involve considerably more time, effort, personnel and cost, compared to single-shot blocks. Liposomal bupivacaine is a long-acting analgesic proposed to provide 72 hours of pain relief, but studies have been disappointing (2.). In a study conducted at our institution, Auricular stimulation, an alternative technique related to acupuncture, has been shown to reduce opioid consumption for the first three days after kidney donation surgery (3). A recent observational study including ambulatory shoulder surgery evaluated the "Bridge" device (manufactured by Masimo, previously FDA approved to reduce symptoms of opioid withdrawal) for postoperative pain control after application of single-shot nerve block (4.). The authors reported a markedly low opioid requirement among the patients, as well as very low postoperative pain scores. The device has proven simple to place, symptom-free, well-tolerated, and easy for patients to wear and remove at home. For these reasons, we would like to further explore the use of this non-invasive, alternative device for pain control among outpatient rotator cuff surgery patients.

The Bridge device, currently FDA approved for opioid use disorder, acts as a peripheral nerve stimulator/modulator. Nerves potentially affected by the electrodes placed on and around the ear include the auriculotemporal branch of the Mandibular Nerve, the posterior auricular branch of the Facial Nerve, the Glossopharyngeal Nerve, and the auricular branch of the Vagus Nerve, as well as the peripheral occipital and greater auricular nerves. This stimulation is believed to provide analgesic effects through influence on various neurotransmitters, including serotonin, norepinephrine and GABA, and has resulted in 56-75% reduction of opioid requirements in major abdominal surgery (4).

The device has an integrated 3 volt battery, with an impedance range of 1 to 10 kilo-ohms. It provides symmetrical, biphasic stimulation at a frequency of 0.125 Hz. Its package notes that it is contraindicated for patients with pacemakers, those with hemophilia (since the electrodes involve a micro-needle puncture), and psoriasis involving the ear. We would broaden this to include any patient with active anticoagulation, or any dermatologic condition involving the skin of the ear where the device would be placed.

Study Hypothesis: Use of the Bridge device will reduce opioid requirements (after resolution of block) by more than 33% on postoperative days 1 through 5.

Primary Outcome: Cumulative Oral Opioid Use (expressed as Oral Morphine Equivalents) on Postoperative days 1 through 5.

Secondary Outcomes: NRS pain scores recorded every four hours on postoperative days 0 to 4,
Oral opioid use on Individual Postoperative days 5 through 7
NRS pain scores recorded every 8 hours on postoperative days 4 to 7
Adverse effects related to opioids (nausea, dizziness, vomiting, itching)
Local adverse effects on ear related to use of bridge device (pain, etc)

Setting: UPMC West Mifflin Ambulatory Surgery Center, West Mifflin, PA. Specifically with use in ambulatory rotator cuff repair patients.

Subjects: We plan to enroll 15 patients in this observational, "proof of concept" study, in order to evaluate whether a 33% reduction in opioid use is possible over postoperative days 1 through five (after resolution of block), as compared to historical controls.

Procedures: Informed consent will be obtained, per IRB requirements. Standard anesthesia will be provided for rotator cuff repair for all patients. This includes single-shot bupivacaine interscalene nerve block with propofol sedation for the surgery itself, followed by application of the Bridge device in consented patients. Application of Bridge device occurs after surgery in recovery area. The ear is scrubbed with alcohol and electrodes placed in the required areas on or just in front of auricle. The device is then activated in the PACU. Patients will fill out a "pain diary" at home to record oral opioid use and pain scores as noted above, for first seven days after surgery. A study coordinator will call the patients on postoperative day 1, 3 and 7 to evaluate them. The device becomes inactive after 5 days and will be removed and discarded. At the end of 7 days, patients will fill out a Quality of Recovery survey, as well as a survey about the impact of the use of the device on their pain and recovery.

Endpoints: These include the primary and secondary outcomes noted above. At the end of five days, the device will be removed by the patient and discarded. Any patient who develops pain or skin irritation (or other adverse reaction) from the Bridge device will be advised to remove it and their participation will be stopped at that time.

Data Analysis: Descriptive statistics will be utilized, including comparison to historic controls. Mean pain values based on recorded NRS score for each postoperative day will be compared between groups. For the primary outcome, opioid ingestion over the entire interval of postoperative days 1 to 5 will be expressed as mean OME for each group, reported with 95% confidence interval. In pain scores, a difference of at least 1.7 on NRS scoring is considered to represent a meaningful clinical difference for shoulder surgery.

1. Abdallah FW Anesth Analg 2015;120:1114.
2. Hussain N. Anesthesiology 2021;134:147
3. [name]. J Complement Integr Med 2021 doi:10.1515/jcim-2021-0208

4. Ilfeld BM Reg Anesth Pain Med 2022;47:581

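### Ear effects are a secondary outcome, but no ear question is planned, contact ends at day 7, and patients with an ear reaction may lose follow-up first

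*Combined protocol and SAP*

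**What the plan says.** **Exposure.** The device description in the Background gives the reason for one contraindication as a skin puncture: "those with hemophilia (since the electrodes involve a micro-needle puncture". The investigators then widen the exclusions: "We would broaden this to include any patient with active anticoagulation, or any dermatologic condition involving the skin of the ear". Under Procedures, the device is placed in the recovery area and becomes inactive after five days. Endpoints adds that the patient takes it off and discards it.

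**Outcome.** Secondary Outcomes lists "Local adverse effects on ear related to use of bridge device (pain, etc". No list of events, grading or assessment times follows.

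**Collection.** The home diary described under Procedures covers oral opioid use and pain scores for seven days. On contacts, Procedures says: "A study coordinator will call the patients on postoperative day 1, 3 and 7 to evaluate them". The content of the calls is not described. A recovery survey and a survey on the device's impact on pain and recovery are completed at the end of day 7.

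**Early stopping.** Endpoints says: "Any patient who develops pain or skin irritation (or other adverse reaction) from the Bridge device will be advised to remove it". The same sentence ends that patient's participation at that point.

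**Afterwards.** No contact after day 7 is described, and no follow-up of an ear event until it resolves.

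**The concern.** A secondary safety outcome needs a definition, a time at which it is asked about, and a record of how each event ended. The plan has a category heading and three calls of unspecified content. The diary, its most frequent source of data, has no place for ear findings.

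The early-stopping sentence makes this worse in a particular direction. Patients with an ear reaction are the ones who supply this outcome, and as written they leave the study when it begins. Duration, worsening and resolution may then go unrecorded for exactly those patients. Someone whose problem is still present at the last call is in a similar position.

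Incomplete capture can only lower the count or shorten the recorded course of an event. The Background already describes the device as easily tolerated. A low count from an unstructured assessment could be read as confirming that, although the plan had not tested it properly.

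**Working it through.** The plan gives no figure for follow-up after removal and no design inputs for its sample of 15, so there is no stated number to reproduce. The check compares the timelines and then asks what one event is worth in a sample of this size.

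**1. Planned observation after the device comes off**

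Inputs: removal at the end of day 5 (Endpoints); last call, diary and surveys at day 7 (Procedures). The day of surgery is taken as day 0.

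| Patient | Device off | Last planned contact | Days observed after removal |
|---|---|---|---|
| Wears device to schedule | day 5 | day 7 | 7 − 5 = 2 |
| Has an ear reaction and stops on day d | day d, or when the patient acts on the advice | participation ends on day d | d − d = 0 |

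The second row takes the stopping of participation to include the stopping of data collection. The documents do not say otherwise.

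**2. Where an ear event could be recorded**

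| Source | Timing | Ear item specified? |
|---|---|---|
| Diary | days 0 to 7 | No: opioid use and pain scores |
| Coordinator calls | days 1, 3, 7 | Content not stated |
| Surveys | end of day 7 | Not stated; one concerns the device's impact on pain and recovery |

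No call falls on the removal day. The calls on either side are days 3 and 7, a gap of 7 − 3 = 4 days.

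**3. What one event is worth with 15 patients**

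Exact two-sided 95% limits:

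- 0 of 15: upper limit = 1 − 0.025^(1/15) = 0.218, or 21.8%.
- 1 of 15: estimate = 1/15 = 6.7%. The lower limit is 1 − 0.975^(1/15) = 0.002. The upper limit solves (1 − p)^15 + 15p(1 − p)^14 = 0.025, giving p = 0.319. The interval is 0.2% to 31.9%.

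One unrecorded event therefore moves the reported rate from 6.7% to 0% and the upper limit from 31.9% to 21.8%.

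**4. Context under assumed event rates**

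The documents give no ear-event rate. The chance of at least one event in 15 patients is 1 − (1 − p)^15:

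- p = 1%: 1 − 0.99^15 = 14%
- p = 5%: 1 − 0.95^15 = 54%
- p = 10%: 1 − 0.90^15 = 79%

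These assume that every event is captured. Few events, or none, are plausible across this range, so the record of each one matters. The figures do not show how many events the present plan would lose.

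**The case against.** The strongest reply is that this is a 15-patient, observational proof-of-concept study about opioid use. Ear effects are one descriptive secondary outcome, and no formal safety conclusion is planned. The outcome is worded openly, with pain as an example, and Endpoints separately mentions skin irritation and other adverse reactions. Bleeding or infection at the ear would already fall within it. The day 7 call comes after scheduled removal and can pick up anything present by then. A wide interval at 15 patients reflects the sample size, and better follow-up would not narrow it.

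Most of this stands, and it limits what can be claimed. A reader might go further in four ways that the documents do not support:

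- **That the outcome is restricted to pain.** It is not; the fault is that it is unspecified.
- **That the documents raise an infection concern for the ear.** They do not. Infection is mentioned once, for nerve-block catheters, which "generally are removed by postoperative day three to avoid infection and due to pump reservoir limitations". That sentence concerns a different device and gives a second reason as well, so comparing its day three with the five days of ear wear says nothing about ear risk.
- **That late complications are certainly missed.** They may be. Nothing in the documents says that ear problems begin after day 7.
- **That calling the device non-invasive is a design fault.** The Background's wish to "further explore the use of this non-invasive, alternative device for pain control" sits awkwardly beside the puncture statement, but reconciling the two is editorial.

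The reply does not answer the early-stopping sentence. An open-ended category does not help if the patient has left the study, and the day 7 call is not planned for someone whose participation has already ended.

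**Conclusion.** The point holds as a gap in specification and follow-up. The ear outcome has no event list, no diary item and no scripted question. Planned observation after removal is two days for patients who wear the device to schedule and none for those stopped by an ear reaction. Ear events may therefore have no recorded course or outcome, and the patients who have them may lose follow-up first.

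The number of events affected is unknown, because neither an event rate nor its timing is given. This rests on two readings: that stopping participation also stops data collection, and that the unscripted calls do not reliably elicit ear findings. If study staff already ask about the ear and keep calling patients who stop, the gap is only in the written plan.

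The change is worth making because it is cheap. Without it, the outcome is incomplete for the patients it describes. It does not call the sample size or the definition of the primary outcome into question.

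**What to change.** 1. At the existing calls on days 1, 3 and 7, ask by name about ear pain, bleeding, skin irritation or breakdown, and signs of infection. Record the onset date of each.
2. State that data collection continues for patients who remove the device early. This leaves the removal rule itself unchanged. It also keeps their opioid and pain records through the planned period.
3. Follow by phone every ear event still open at early stopping or on day 7 until it resolves, recording an end date and outcome.
4. Report ear events over all patients who had a device placed, with an exact 95% interval.

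A closing contact with all 15 patients at a set time after day 7 is optional. Reconciling the non-invasive description with the puncture statement is a wording change.

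The cost is a few call-form items, a protocol sentence or two, and extra calls to the patients with an open event or early removal. The downside is slightly longer participation for those patients and possibly a less favourable ear-event rate.

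### Pre-operative opioid use is neither restricted nor recorded for the 15 Bridge patients and is not mentioned for the historical controls, so an imbalance in regular users could move the 33% comparison either way, unidentified

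*Combined protocol and SAP*

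**What the plan says.** The patient restrictions appear in the device description under Background. The package contraindications are pacemakers, hemophilia and psoriasis of the ear. The investigators add: "We would broaden this to include any patient with active anticoagulation, or any dermatologic condition involving the skin of the ear". None of these concerns opioid use. Setting adds only that patients have ambulatory rotator cuff repair.

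Under Procedures, patients complete a diary "at home to record oral opioid use and pain scores as noted above, for first seven days after surgery". A coordinator calls on days 1, 3 and 7, and two surveys follow at day 7. No pre-operative opioid item is described.

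The Study Hypothesis is that the device "will reduce opioid requirements (after resolution of block) by more than 33% on postoperative days 1 through 5". The Primary Outcome is cumulative oral opioid use in OME over those days. Under Subjects: "We plan to enroll 15 patients in this observational" study, compared with historical controls. Data Analysis says "Descriptive statistics will be utilized, including comparison to historic controls", and for the primary outcome "opioid ingestion over the entire interval of postoperative days 1 to 5 will be expressed as mean OME for each group", with a 95% confidence interval.

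The document does not give the source, number, eligibility or opioid history of the historical controls.

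**The concern.** The outcome counts every oral opioid taken on days 1 to 5. No rule separates a drug the patient already took at home from a drug taken for surgical pain. The phrase about block resolution limits the time window, not the source of the opioid. The mentions of opioid withdrawal and opioid use disorder describe the device's approval and are not entry criteria.

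The groups are not randomised, and no matching, stratification or adjustment is planned, so nothing balances the share of regular users. In a mean of 15, one patient carries one fifteenth of the weight. If regular users are more common in one group, the apparent reduction moves for a reason unrelated to the device. Because the Bridge patients are not asked about earlier use, the data could not show afterwards that this had happened. What is at stake is how the study's one quantitative question, the 33% comparison, is read.

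**Working it through.** **The plan's own figures.** There is no calculation to reproduce. The documents give 15 patients, a 33% target and days 1 to 5, but no OME mean, SD, control number or share of regular users. All OME values below are therefore assumptions.

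**Inputs.** n = 15 (Subjects). Five-day means without regular users, Bridge b and control c: 50 and 75 mg, or 100 and 150 mg; both pairs give a true reduction of 1 − b/c = 33.3%. One regular user takes the place of one patient and takes U = 150, 200 or 300 mg in total over five days (30, 40 or 60 mg/day), with no device effect on that user. The other 14 patients have SD s = b/2. The control mean is treated as fixed. t(14) = 2.145.

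**User in the Bridge group only.**
- Mean: m = (14b + U)/15. Observed reduction: 1 − m/c. Shift: 33.3% minus that.
- Half-width with the user included: SS = 13s² + 14(b − m)² + (U − m)²; SD = √(SS/14); half-width = 2.145 × SD/√15, divided by c to give percentage points.

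| b vs c (mg) | U (mg) | m (mg) | Observed reduction | Shift (points) | 95% half-width (points) |
|---|---|---|---|---|---|
| 50 vs 75 | 150 | 56.7 | 24.4% | 8.9 | 26.1 |
| 50 vs 75 | 200 | 60.0 | 20.0% | 13.3 | 33.7 |
| 50 vs 75 | 300 | 66.7 | 11.1% | 22.2 | 50.9 |
| 100 vs 150 | 150 | 103.3 | 31.1% | 2.2 | 18.4 |
| 100 vs 150 | 200 | 106.7 | 28.9% | 4.4 | 20.2 |
| 100 vs 150 | 300 | 113.3 | 24.4% | 8.9 | 26.1 |

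Third row in full: SS = 13 × 625 + 14 × 16.67² + 233.33² = 8,125 + 3,889 + 54,444 = 66,458. SD = √(66,458/14) = 68.9. Half-width = 2.145 × 68.9/√15 = 38.2 mg, and 38.2/75 = 50.9 points. The shift is 22.2/50.9 = 44% of the half-width, the largest ratio of the six. All six intervals contain 33.3%.

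**Users among the controls only** (share 1 in 15, U = 300 mg). The control mean becomes (14 × 75 + 300)/15 = 90 mg or (14 × 150 + 300)/15 = 160 mg. A true 33.3% then appears as 1 − 50/90 = 44.4% or 1 − 100/160 = 37.5%. With no true effect, the false reduction is 1 − 75/90 = 16.7% or 1 − 150/160 = 6.3%.

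**Same 1-in-15 share in both groups** (U = 300 mg). 1 − 66.7/90 = 25.9%, or 1 − 113.3/160 = 29.2%. If the device also cuts the user's intake by a third, to 200 mg, the result is 1 − 60/90 = 33.3% or 1 − 106.7/160 = 33.3%: no distortion.

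**Chance imbalance.** If the share is 1/15 in both populations, 15 Bridge patients contain no user with probability (14/15)^15 = 36%, one with 15 × (1/15) × (14/15)^14 = 38%, and two or more with 26%.

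**What the proposed analysis does** (50 vs 75 mg). Removing users from both groups gives 1 − 50/75 = 33.3%, or 1 − 75/75 = 0% if there is no effect. Removing them from the Bridge group only, while the controls keep a 1-in-15 share at 300 mg, gives 1 − 50/90 = 44.4%, or a false 1 − 75/90 = 16.7%.

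**The case against.** The strongest reply is that this is a small, descriptive proof-of-concept study, that total oral OME is a legitimate outcome, and that nothing shows any regular user will be enrolled. Pre-operative opioid use is also only one of many baseline items that the document does not list. All of this stands. It limits the weight of the point but does not close the gap, because the 33% comparison is the stated hypothesis and earlier opioid use feeds directly into the quantity measured.

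The reply also holds on three stronger readings that a reader might infer:

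- **That one user's shift can exceed sampling error.** Setting SD at half the Bridge mean and leaving the user out gives 2.145 × 25/√15 = 13.8 mg, or 18.5 points, which the 22.2-point shift exceeds. But that user is in the sample and widens the interval. With the user included, no shift passes 44% of the half-width.
- **That the bias most likely hides a benefit.** This follows only if one control user is held fixed while the control group grows, so that the share falls. At a constant share the control-side error does not shrink. The documents do not describe the controls, so the direction is unknown.
- **That one user will generally defeat the hypothesis.** The table starts at a true 33.3%, on the threshold, where almost any excess crosses it. The Background cites reductions of 56 to 75% in major abdominal surgery. From 56% or 75%, with the same users and control means, 11 of 12 scenarios stay above 33%. The exception is 56% with a 75 mg control mean and a 300 mg user: b = 33, m = (14 × 33 + 300)/15 = 50.8, and 1 − 50.8/75 = 32.3%.

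**Conclusion.** The point holds as a gap in planned data and comparability. Followed as written, the plan counts home opioid as post-surgical use, and an imbalance in regular users could move the 33% comparison in either direction without planned data to identify it. With one Bridge user and a true effect on the threshold, the shift is 2.2 to 22.2 points. The planned interval would show such a result as imprecise, but not why.

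These sizes rest on assumed means, SD and user intake, a fixed control mean and no device effect on the user. The documents confirm none of these.

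A reader might also infer that the study could falsely confirm its hypothesis through this route. That is unlikely from this source alone. With no true effect and a 1-in-15 control share, a false 33.3% needs 15 × 112.5 − 14 × 75 = 637.5 mg (127.5 mg/day) from each such user at a 75 mg mean, or 15 × 225 − 14 × 150 = 1,275 mg (255 mg/day) at 150 mg. The point supports a cheap improvement to the plan, not a claim that the study's result would be invalid.

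**What to change.** - Record pre-operative daily opioid use, in OME, at consent.
- Define a regular user before enrolment starts.
- Extract the same item for the historical controls where their records allow.
- Report the primary mean OME and 95% confidence interval with and without regular users in both groups.
- If the control data are missing, say so and label the result without users as not like-for-like, because removing users from the Bridge group alone biases towards benefit.

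The cost is one baseline question, a check of the control records and one extra descriptive analysis. The control data may prove incomplete. The primary outcome, sample size and enrolled population need not change.

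### Does listing individual-day opioid use only from POD 5, with postoperative-day boundaries undefined, leave the plan unable to relate opioid use to the active device?

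*Combined protocol and SAP*

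**What the plan says.** The Primary Outcome is "Cumulative Oral Opioid Use (expressed as Oral Morphine Equivalents) on Postoperative days 1 through 5", and the Study Hypothesis uses the same window: "Use of the Bridge device will reduce opioid requirements (after resolution of block) by more than 33% on postoperative days 1 through 5". Data Analysis reports this total as one mean per group with a 95% confidence interval. Under Secondary Outcomes, the only opioid measure by day is "Oral opioid use on Individual Postoperative days 5 through 7".

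On device timing, Procedures states "The device is then activated in the PACU" and later "The device becomes inactive after 5 days and will be removed and discarded". Endpoints repeats the point: "At the end of five days, the device will be removed by the patient and discarded".

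On data, patients keep a home diary "to record oral opioid use and pain scores as noted above, for first seven days after surgery". Pain gets a daily analysis: "Mean pain values based on recorded NRS score for each postoperative day will be compared between groups". Secondary Outcomes starts pain scoring at POD 0, so the protocol's numbering includes a day zero. No section gives a clock time or an hour count at which a postoperative day starts or ends.

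**The concern.** Individual-day opioid reporting appears to begin about when stimulation ends. Opioid use on POD 1-4 enters only through a five-day sum, although pain, a secondary outcome, is compared for each day. In a 15-patient proof-of-concept study against historical controls, one would like to see whether any reduction is present while the device is active and changes when it stops.

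The missing day definition adds to this. Activation is on the day of surgery and the device lasts five days, so expiry falls inside POD 5, at its start or at its end, depending on how days are counted. If benefit ceases at expiry, the off-device part of POD 5 pulls the POD 1-5 reduction below the on-device reduction. The hypothesis asks for more than 33%, so a few points could affect how the result is read.

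**Working it through.** **1. What the listed outcomes already give.** Take the device's active life as 120 hours from activation (five days; the exact hours are an assumption).

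| Convention | POD 1-4 | POD 5 | POD 6-7 |
|---|---|---|---|
| Calendar days | on-device | mixed | off-device |
| 24-hour blocks, POD 0 = hours 0-24 | hours 24-120, on-device | hours 120-144, off-device | off-device |
| 24-hour blocks, POD 1 = hours 0-24 | hours 0-96, on-device | hours 96-120, on-device | off-device |

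The third row fits poorly with a protocol that uses a POD 0. For each patient with complete data:

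POD 1-4 total = (cumulative POD 1-5) − (individual POD 5).

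Both terms on the right are listed outcomes. They give an on-device total under every row, and POD 6 and POD 7 are listed as separate off-device days. The listed opioid outcomes therefore do span expiry. Only the split among POD 1, 2, 3 and 4 is not listed.

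**2. How much of POD 5 is off-device.**
- Calendar days, activation at clock hour t: off-device hours = 24 − t. With t assumed between 8 and 18, this is 16 down to 6 hours, or 67% to 25% of POD 5. Against the 120-hour primary window it is 16/120 = 13.3% down to 6/120 = 5%.
- 24-hour blocks from POD 0: 24 of 24 hours, or 100% of POD 5 and 24/120 = 20% of the window.
- 24-hour blocks from POD 1: none.

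**3. Effect on the primary figure.** The documents give no daily-use profile, activation hour or carry-over, so all three are assumed here. Let f be the on-device fraction of POD 5, c the share of benefit that persists after expiry, and s POD 5's share of POD 1-5 use: 0.20 if use is flat, 0.10 if it declines 30/25/20/15/10%. With a 33% on-device reduction:

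Observed reduction = 33% × [(1 − s) + s × (f + (1 − f) × c)].

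Example, flat use, activation at 09:00 (f = 9/24 = 0.375), c = 0: 33% × (0.80 + 0.20 × 0.375) = 28.9%.

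| Case | Flat use | Declining use |
|---|---|---|
| Calendar days, 09:00-16:00, c = 0 | 28.9-30.8% | 30.9-31.9% |
| Calendar days, 09:00-16:00, c = 0.5 | 30.9-31.9% | 32.0-32.5% |
| Blocks from POD 0, c = 0 | 26.4% | 29.7% |
| Blocks from POD 0, c = 0.5 | 29.7% | 31.4% |
| Blocks from POD 1, or c = 1 | 33.0% | 33.0% |

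The largest shift, 33.0 − 26.4 = 6.6 points, needs flat use, no carry-over and blocks from POD 0 together. With calendar days and no carry-over the shift is 1.1 to 4.1 points.

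**4. Scale against sampling error.** With n = 15, the 95% half-width for a mean is 2.145/√15 = 0.554 times the SD. For an assumed coefficient of variation of 0.5 to 1.0, that is 28% to 55% of the device-group mean. After a 33% reduction it is 0.67 times as much, about 19% to 37% of the control mean. The possible dilution is small beside this.

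**The case for a change.** The best argument for a change is that the rationale is about timing. Background describes pain returning when a single-shot block ends, and cites an earlier study of auricular stimulation with lower opioid use over the first three days. A five-day sum, or a four-day sum obtained by subtraction, cannot show when within the active period a reduction occurs. The diary already holds the data, so listing daily opioid use for POD 1-7 would cost little, and naming it in advance would avoid the charge that days were picked after seeing 15 patients' results.

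Part of this stands. The shape within POD 1-4 is not a listed outcome, and the day boundaries are not written down. But the gain is limited. In a single treated group a daily profile mixes device effect with ordinary recovery, and showing a reduction day by day needs daily data from the historical controls, which the documents do not say exist. Descriptive statistics are the planned method, so daily summaries are not ruled out. A supportive POD 1-4 figure is already obtainable, and its 33.0% in the calculation only restates the assumed on-device effect. Recording the removal time would not settle the mixed day either: the device goes inactive regardless of wear, so the activation hour governs how much of POD 5 is off-device.

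**Conclusion.** No change to the plan is needed. The text is as described: no daily opioid outcome is named for POD 1-4, and postoperative days have no stated boundaries. The main consequence does not follow, because cumulative POD 1-5 and individual POD 5-7 together give an on-device total and separate off-device days. A cumulative figure for roughly the device period, followed by single days around and after expiry, is a coherent choice.

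The boundary definition is a detail that analysts must settle when they turn diary entries into days, and a sensible reading is at hand because the protocol uses a POD 0. Its effect on the primary is at most 6.6 points in the cases computed, and 1.1 to 4.1 points with calendar days and no carry-over. These figures rest on 120 hours of activity and on assumed activation times, use profiles and carry-over. Any such difference is toward no effect. It is also not an error in the estimate: the hypothesis is stated for POD 1-5, so whatever POD 5 contains is part of the quantity the study set out to measure. Following the plan as written leads to no wrong result, threshold or conclusion.

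### The outcome list attributes nausea, dizziness, vomiting and itching to opioids in advance and has no outcome for non-local device effects, so a systemic device reaction could be mislabelled or left uncounted

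*Combined protocol and SAP*

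**What the plan says.** Two lines under Secondary Outcomes deal with harm:

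- "Adverse effects related to opioids (nausea, dizziness, vomiting, itching"
- "Local adverse effects on ear related to use of bridge device (pain, etc"

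The device description in the Background lists, among the nerves that may be affected, "the Glossopharyngeal Nerve, and the auricular branch of the Vagus Nerve". It attributes the hoped-for analgesia to "influence on various neurotransmitters, including serotonin, norepinephrine and GABA".

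The Endpoints section has a removal rule that is wider than the ear: "Any patient who develops pain or skin irritation (or other adverse reaction) from the Bridge device will be advised to remove it". Participation then ends.

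On data collection, the Procedures section gives patients a diary "to record oral opioid use and pain scores as noted above, for first seven days after surgery". It adds: "A study coordinator will call the patients on postoperative day 1, 3 and 7 to evaluate them". What the calls ask is not stated. At seven days there is a recovery survey and a survey on the device's impact.

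**The concern.** The first safety line assigns cause by type of symptom and the second assigns it by location. Neither provides for a symptom away from the ear that the device may have caused. No outcome covers adverse events regardless of cause, and no method is given for judging cause.

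This matters because the plan proposes that the device works through nerve pathways and neurotransmitters, not only at the skin. A device expected to have benefits away from the ear cannot be assumed to have side effects only at the ear. The plan also studies it for a use other than the approved one that it names, and the Background already describes it as easy to tolerate. At stake is whether the safety statement from this study can be taken at face value. A low device-event count could reflect how the outcomes are labelled as much as what happened to patients.

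**Working it through.** No stated figure is at issue, so the main check is to trace possible events through the text.

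| Event while the device is worn | Secondary outcome that takes it | Endpoints removal rule |
|---|---|---|
| Pain or irritation at the ear | Local device line | Applies |
| Itching at the electrode site | Local device line, which is open-ended | Applies if attributed to the device |
| Nausea, dizziness, vomiting or general itching, opioid taken | Opioid line | Applies only if attributed to the device |
| The same symptoms, no opioid taken | Opioid line if read by symptom; none if read strictly by cause | Applies only if attributed to the device |
| Any other non-local reaction | None | Applies only if attributed to the device |

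The last three rows show the gap. For the four named symptoms, the only available outcome carries an opioid label. For any other systemic reaction there is no outcome. The removal rule may identify such a reaction, but only after someone has judged the device responsible, and no outcome then counts it.

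**Timing.** Under Procedures, the device is activated in the recovery area after a single-shot interscalene block. The hypothesis concerns opioid need once the block has worn off. Device exposure may therefore precede opioid use, and a symptom in that interval would still have only the opioid line. The hypothesis also expects opioid use to fall by more than 33%. The better the device works, the less plausible the opioid label becomes.

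**Could another part of the design reveal a misattribution?** There is no concurrent or sham arm. Data Analysis names group comparisons only for mean pain scores and mean opioid use, and nothing says the historical controls have side-effect data. As an illustration, assume that they do, that there are 15 of them, that background nausea is 20% to 40%, and that the device adds 10 to 20 percentage points. None of these values is in the documents. The power of a two-sided 0.05 comparison of 15 with 15 is then about 8% to 22%:

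| Background rate | Device adds 10 points | Device adds 20 points |
|---|---|---|
| 20% | 9.1% | 21.7% |
| 30% | 8.2% | 19.5% |
| 40% | 7.8% | 18.9% |

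**What 15 patients can say about device events** (n = 15 from the Subjects section):

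- One event: 1/15 = 6.7%, exact 95% interval 0.2% to 31.9%.
- No events, two-sided 95% upper limit: 1 − 0.025^(1/15) = 21.8%. One-sided: 1 − 0.05^(1/15) = 18.1%.
- Chance of at least one event: 1 − 0.95^15 = 53.7% at an assumed true rate of 5%, and 1 − 0.90^15 = 79.4% at 10%.

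These limits hold for 15 patients under any labelling. They show that one or two events carry much of the information, but not how many would be mislabelled.

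**The case against.** The strongest reply is that the plan does not ignore non-local device harm. The removal rule covers any adverse reaction from the device, so such a reaction could surface as a discontinuation. The calls on days 1, 3 and 7 and the day-7 device survey could also pick it up. An event under the opioid heading would still be reported as nausea or dizziness. The study is small and descriptive, and its aim is opioid reduction, not device safety.

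Much of this stands, and it rules out several stronger readings that a reader might infer:

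- That a systemic device effect will be reported as an opioid effect, or cannot be recorded at all. The text does not settle this; there is partial capture through removals and calls. The effect could be mislabelled or left uncounted.
- That itching at the electrode site is misfiled. The local line is open-ended and already accommodates it.
- That the device causes nausea or dizziness. The plan describes nerves that may be affected and a mechanism that is believed to operate. It links neither to these symptoms.
- That a comparison of opioid side effects with controls is biased. No such comparison is specified.

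The reply does not close the gap. The removal rule is not an outcome, it depends on a causal judgement for which no method is given, and no outcome counts what it finds. The calls have no stated symptom content, and the diary is described as covering opioid use and pain scores only.

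**Conclusion.** The concern holds as a defect in how outcomes are classified. Secondary Outcomes and Endpoints do not match: Endpoints foresees device reactions that are not confined to the ear, and Secondary Outcomes has no line for them while assigning four systemic symptoms to opioids in advance. A systemic device reaction could be labelled an opioid effect or counted nowhere, and a historically controlled study of 15 patients would be unlikely to show that this had happened.

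The number of events affected cannot be estimated from the documents. Each one would move the device count by 1 in 15. The conclusion assumes only that a non-local device effect is possible on the plan's own description of the device. It does not assume that one occurs. The primary outcome is untouched, but the safety statement is weakened, and the correction is cheap enough to be worth making.

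**What to change.** 1. Replace the opioid-related line with nausea, vomiting, dizziness and itching from any cause. For each report, note the day, whether the device was in place, and whether an opioid had been taken. Present the results without a presumed cause.
2. Widen the device line to any adverse reaction judged possibly related to the device, local or systemic, including every reaction that led to removal, so that it agrees with Endpoints. State which study role makes that judgement.
3. If symptoms are tabulated by preceding opioid use, call the table descriptive. It cannot establish cause: surgery, sedation and the block are other possible causes, and there is no concurrent arm. An any-cause count has the same limit, but it does not hide it behind a label.

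Cost: a symptom line in the diary and symptom questions at the three planned calls, with no added visits. The documents describe no call script, so the questions would have to be written. The device-event count may look less favourable than under the present wording.
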